### **Repeated Measures**

Barring study withdrawal or death (or hospice transfer), each participant will be assessed at multiple time points. Participants may be clustered by VA provider and/or SNF discharge location. Thus, outcome measurements may exhibit heterogeneity across participants and clusters. Our statistical plan takes full advantage of this information by using a mixed-effects framework for each analysis. In the event that a mixed-effects technique cannot be implemented, an alternative method will be used, and the standard errors of effect estimates will be adjusted using the robust Huber-White ‘sandwich’ method.

## **DATA MANAGEMENT AND QUALITY ASSURANCE**

### **Data Collection Forms & Data Entry**

The study team chose to utilize hard copy case report forms to allow for quality assurance reviews of entered data. The standardized interview and abstraction forms were approved by the IRB. Data recorded on the case report forms are entered into a VA REDCap database. Assessment and interview forms are entered within the same week of data collection, and if possible, the same day.

### **Data Storage**

Paper data collection forms are stored in locked filing cabinets in the academic partner’s offices. Upon study completion, each Veterans files are moved to the local VA research offices where they are stored in a locked filing cabinet. Electronic data is stored in the VA REDCap and on a shared project folder only accessible to study team members. With permission of the IRB, de-identified data is allowed to be temporarily stored on the secure server of the academic partner. All electronic files are username and password protected. Data in the REDCap databases and secure server will be stored indefinitely to all for subsequent data analyses.

### **Quality Assurance**

No quality assurance training or metrics are required beyond standard IRB Human Subjects training. To ensure data integrity, the project coordinator will conduct weekly data reviews to check for completion and accuracy.

## **PARTICIPANT RIGHTS AND CONFIDENTIALITY**

The DROP trial’s intervention is considered human subjects research and is subject to standard review by the local institutional review board (IRB). All protocols, consent forms, and other research materials were submitted and approved prior to the recruitment of any Veterans. As noted above, the study is subject to an annual safety review by the IRB. All study personnel complete annual human subjects and good clinical practice training. Below is a summary of key human subjects information submitted to the IRB.

### **Protection Against Risks**

The deprescribing intervention protocol is a carefully developed, multi-stage process that includes the independent review of multiple clinicians, each of whom can stop any recommended deprescribing action. This includes the research team pharmacist or nurse practitioner, primary hospital team, and the Veteran or their surrogate. Each medication recommended for deprescribing will be considered for its potential for physiologic withdrawal, pharmacokinetic/pharmacodynamic effects, and medical condition exacerbation. Strategies to protect against risks are as follows:

- Any medication believed to have increased potential for physiologic withdrawal will undergo a prescribed drug taper, where the identified drug will not be reduced by more than 25% to 50% during any 1-week interval when a patient is receiving greater than the minimum therapeutic dose.

- Deprescribing pharmacists / NPs will alert the primary medical team and make recommendations to the post-acute care for surveillance of symptoms, signs (e.g., vital signs), labs (e.g., electrolytes, INR), or follow-up tests (e.g., EKG).
- A strength of this trial is that we will be able to monitor for exacerbations of medical conditions in a post-acute care setting (mean length of stay = 26.9 days), where monitoring of vital signs and symptoms are done daily by licensed nurses. In addition, during the “SNF handover” process, all discontinued medications will be clearly delineated along with any expected signs or symptoms that may be expected to return.
- Medications can be restarted or increased at any time should adverse pharmacokinetic/pharmacodynamics effects or a physiologic drug withdrawal effect be detected.

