### Study Population and Sample Size

Eligible Veterans are age  $\geq 50$  with polypharmacy as defined by  $\geq 5$  medications based on the pre-hospital admission; ability to provide consent (or proxy); speaks English; does not reside in long-term care or receive hospice services; have a recommendation or referral to a skilled nursing facility (SNF). All eligible Veterans will be approached for consent with an original enrollment goal of 540.

The population and sample size were adjusted mid-study due to the significant enrollment and retention challenges caused by the COVID-19 pandemic. It was determined that a sample of 260 Veterans was sufficient to provide power greater than 93% for both the primary and secondary outcomes. Additionally, Veterans who were recommended SNF placement but ultimately discharged from hospital to home were approved to remain in study, which improved the study retention rate.

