## STUDY PROCEDURES

Data collection includes Veteran descriptive data along with geriatric syndromes, medications, health status, safety, and implementation science as noted in the table below. Upon enrollment, the Veteran will complete interviewer-administered questionnaires (marked with an asterisk below) with interviews conducted by trained study personnel. In the event the Veteran is unable to complete assessments (e.g., delirious, cognitively impaired), their designated surrogate will be asked to complete the assessments for which surrogate responses have been validated. Assessments that can be completed by surrogates are the ICIQ (urinary incontinence), DETERMINE, falls, pressure ulcers, medication history, and demographics. The remainder of the data will be abstracted from each patient's medical record; however, total number and type of medications will be determined based on a

combination of patient interview, medical record and pharmacy refill history to ensure an accurate, complete medication list.

The data shown in the below table for the “SNF” column is abstracted from SNF medical records; thus, research personnel will not interview the participant again during their SNF stay. However, participants will be contacted via telephone by research personnel at 7 and 90 days after they leave the SNF. If the Veteran is willing to also complete our implementation evaluation interview to assess barriers and enablers of deprescribing during their routine 7-day follow-up call, we will conduct this additional interview at the current 7-day follow-up timepoint in conjunction with other 7-day assessments. However, in consideration of Veteran response burden, we will provide the Veteran with the option to schedule the implementation evaluation interview component anytime during the initial 14-days following SNF discharge, based on the preference and convenience of the Veteran, so that they may choose to complete this interview separately. Both the intervention and control group will be monitored using that same data collection schedule and measures.

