## **SNF Handover**

Within 24-hours of hospital discharge the study team will contact the SNF admissions nurse to review the Transfer Medication List in conjunction with the list of deprescribed medications and the need for medication-specific monitoring, if applicable. In addition, recommended dose titrations may be highlighted during this SNF handover.

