## **Post-Intervention Follow-Up**

The intervention ends at hospital discharge. Originally, if the Veteran discharged to any location other than SNF, they were discontinued from study. Due to retention concerns, the IRB approved the retention of Veterans who discharged home (beginning in March 2021).

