### **Skilled Nursing Facility (SNF)**

The study team will contact the SNF weekly to monitor the Veteran's expected discharge date and monitor for any unplanned healthcare utilization. At the point of SNF discharge, the study team will request the Veteran's discharge medication list.

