### **7- and 90-Day Follow-Up**

The 7-Day follow-up call occurs 7 days after SNF discharge ( $\pm 3$  days), and the 90-Day call occurs 90 days after SNF discharge ( $\pm 10$  days). The study NP or PharmD asks the Veteran to have their medication bottles, pill organizer, and list nearby during the call. If a surrogate assists with medication management, we also ask that person to be available. The Veteran lists of the medications they are currently taking with the dose and frequency information. Afterwards, the study clinician will inquire about medications from enrollment or discharge lists that the Veteran did not address in order to confirm their usage or discontinuation. After the medication history is obtained, the study team administers the geriatric syndrome and medication adherence assessments.

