### **Methods and Timing for Assessing, Recording, and Analyzing Safety Parameters**

#### **Notification of Unplanned Healthcare Utilizations and Deaths**

Unplanned healthcare utilization (intensive care unit transfers, emergency department visits and/or hospitalizations) and deaths are monitored throughout all study phases for each Veteran. The study coordinator and research assistant share a study patient panel in the electronic health record. Any time a participant is admitted to the Nashville VA Medical Center, they are alerted. To identify if a Veteran experience an unplanned healthcare utilization at an outside hospital (OSH), the Veterans are asked at each follow-up time point if they have been to an emergency room or had an inpatient stay, and if so, at what facility. Additionally, the research assistant or study clinician reviews VISTA for any uploaded OSH records at the time of the follow-up calls. The research assistant is responsible for requesting medical records from OSHs (and SNFs) relevant to the utilization.

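### Veterans discharged home stay in the study, but no one outside the hospital is named to receive their medication-specific monitoring needs

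*Combined protocol and SAP*

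**What the plan says.** Study Population and Sample Size records that "Veterans who were recommended SNF placement but ultimately discharged from hospital to home were approved to remain in study". Post-Intervention Follow-Up gives the date: "the IRB approved the retention of Veterans who discharged home (beginning in March 2021". Before that, a Veteran who left hospital for anywhere other than a SNF was discontinued.

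The post-discharge text is written for Veterans in a SNF:

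- Protection Against Risks presents it as a strength that "we will be able to monitor for exacerbations of medical conditions in a post-acute care setting". It describes that setting by a mean stay of 26.9 days and daily checks by licensed nurses, and adds that the SNF handover will set out the discontinued medications and the symptoms that might return.
- SNF Handover says that within 24 hours "the study team will contact the SNF admissions nurse to review the Transfer Medication List", together with the deprescribed medications and any medication-specific monitoring. Dose titrations may be raised at the same time.
- Skilled Nursing Facility (SNF), under Post-Intervention Follow-Up, says "The study team will contact the SNF weekly" about the expected discharge date and unplanned utilization.
- Follow-up is timed from leaving the SNF: "The 7-Day follow-up call occurs 7 days after SNF discharge" (window 3 days either side), with a 90-day call (10 days either side). Study Procedures agrees: "participants will be contacted via telephone by research personnel at 7 and 90 days after they leave the SNF".

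**The concern.** Deprescribing does not always finish at the hospital door. The action list under Pre-Review includes stopping a drug at a set time after discharge and reducing it gradually, under monitoring, until it is stopped. Protection Against Risks caps the weekly dose reduction for drugs with withdrawal potential, so a taper can outlast the admission. For a SNF Veteran, the admissions nurse is told what to watch for. For an intervention Veteran who goes home, the plan names no one in the community to be told.

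Two other protections depend on someone noticing a problem. A medication can be restarted or increased at any time, but only once an effect has been detected. Outside-hospital events are sought when "the Veterans are asked at each follow-up time point if they have been to an emergency room or had an inpatient stay" and when uploaded outside records are checked at the calls. Only an admission to the Nashville VA raises an alert without a call, and for a Veteran who never enters a SNF the calls have no stated starting point.

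At stake is whether a withdrawal effect or a worsening condition in an intervention Veteran at home is recognized early, and whether the protocol describes its safeguards accurately for everyone it retains.

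**Working it through.** The plan gives no figure to reproduce. The check sets each post-discharge element beside the two destinations, then works out a timeline.

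| Element (section) | Discharged to SNF | Discharged home |
|---|---|---|
| Taper limits, clinician and Veteran veto, restart (Protection Against Risks) | applies | applies |
| Alert to primary medical team (Protection Against Risks) | applies | applies |
| Accurate discharge list (Final Deprescribing Actions) | applies | applies |
| Utilization and death tracking, with a signed release for outside records (Safety Outcomes; Notification of Unplanned Healthcare Utilizations and Deaths) | applies | applies |
| Daily checks by licensed nurses (Protection Against Risks) | applies | cannot apply |
| 24-hour handover of monitoring needs, intervention arm (SNF Handover) | SNF admissions nurse | no recipient named |
| Weekly study contact (Skilled Nursing Facility) | with the SNF | none stated |
| Starting point for the 7- and 90-day calls, both arms (7- and 90-Day Follow-Up; Study Procedures) | SNF discharge | none stated |

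The first four rows cover both groups; the last four do not. The missing recipient matters most, because it concerns drugs still being withdrawn. The materials for filling it exist: Description of Assessments records outpatient providers at baseline, and Preliminary Data says the pilot gave its recommendations to outpatient providers as well as the inpatient team. The trial's intervention text names only the inpatient team and the SNF or post-acute side.

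Timeline, using the mean stay of 26.9 days. Its source is not stated, so it is illustrative only.

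- Weekly contacts with the SNF: 26.9 / 7 = 3.8, so three or four.
- First call for a SNF Veteran: 26.9 + 7 = 33.9 days after hospital discharge (30.9 to 36.9).
- Second call: 26.9 + 90 = 116.9 days (106.9 to 126.9).
- Veteran at home, if hospital discharge is the starting point (an assumption; the plan does not say): day 7 (4 to 10) and day 90 (80 to 100).
- Difference: 33.9 − 7 = 26.9 days at the first call and 116.9 − 90 = 26.9 days at the second.

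Counting from hospital discharge would therefore bring the first call to a Veteran at home about 27 days earlier after hospital discharge than at the mean SNF stay.

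**The case against.** The strongest reply is that Veterans at home are far from unprotected. The alert to the primary medical team, with advice on symptoms, signs, laboratory tests and follow-up tests, does not depend on SNF placement. Safety Outcomes commits the team to follow utilization inside and outside the VA. Retention did not create the exposure: these Veterans would previously have been discontinued, so keeping them adds follow-up. The weekly SNF contacts are not clinical checks for withdrawal, and Study Procedures says participants are not interviewed again during the SNF stay. For a Veteran who never enters a SNF, counting the calls from hospital discharge is the obvious reading.

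Most of this stands. The call date is largely a gap in wording. A reader might infer that Veterans at home have no safety monitoring, or that harm was missed; the documents support neither.

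The reply does not supply the recipient. The primary medical team may well be the inpatient team, whose role ends at discharge. The post-acute side mentioned in the same bullet could be stretched to home services, but the next bullet describes that setting by length of stay and licensed nurses. The commitment to track outside utilization names no detection route beyond those tied to the calls.

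Finally, Participant Rights and Confidentiality introduces this material as a summary of what went to the IRB. A home procedure may exist in amendment papers not included here. What can be said is that none is stated in this document.

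**Conclusion.** The concern holds as a specific, inexpensive safety improvement. The protocol retains Veterans discharged home, yet daily nursing, the handover of monitoring needs and the weekly contact are still written for SNF Veterans. For intervention Veterans at home, no outpatient recipient of medication-specific monitoring needs is named, although some deprescribing actions continue after discharge. The undefined starting point for the calls, in both arms, is a lesser matter of clarification; it bears on safety because outside-hospital events are sought at those calls.

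The size cannot be put as a number of Veterans, because the number discharged home is not given. The contrast in procedure is three or four weekly facility contacts at the mean SNF stay against none stated at home. This rests on the illustrative 26.9-day mean and on reading the post-acute wording as meaning a facility.

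**What to change.** 1. For intervention Veterans discharged home, within 24 hours of hospital discharge, send the list of deprescribed medications, any taper schedule and the medication-specific monitoring needs to the outpatient provider already on record and to the Veteran or surrogate. The clinical content is for the investigators to settle.
2. In Protection Against Risks, limit the post-acute monitoring sentence to Veterans in a SNF.
3. State that, for Veterans discharged home in both arms, the 7- and 90-day calls are counted from hospital discharge with the existing windows, and record which starting point was used.

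If a home procedure was already approved, state it instead. Study Design gives enrollment closing in November 2022 and follow-up ending in March 2023; if those dates have passed, report the procedure and starting point actually used.

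The cost is a few more study-clinician contacts and some wording. Home calls would fall about 27 days earlier after hospital discharge than at the mean SNF stay. Because destination is determined after randomization, recording the starting point describes that difference but does not remove it. Randomization, Intent-to-Treat, & Safety Outcomes, as written, limits the analyses to Veterans discharged to SNF, so any use of the home data would first need that sentence settled.

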## Veteran Confidentiality

Research subjects' identities will be kept confidential at all times. Subject identifiers will never be revealed in publication, presentation, or other scientific purpose. All data obtained with subject identifiers will be maintained in locked file cabinets and locked offices on the VA Medical Center (GRECC offices) campus or the academic partner. All study subjects will be assigned a unique study identification number for use in computer database and analytic work. Linkage of patient study IDs to patient identifiers will be maintained by the PIs and Project Coordinator with username/password protected access.

